5.3 PROCEDURES FOR ELICITING, RECORDING, AND REPORTING ADVERSE EVENTS

Eliciting Adverse Events

A consistent methodology for eliciting AEs at all subject evaluation time points should be adopted. Examples of non-directive questions include:

- “How have you felt since your last clinical visit?”
- “Have you had any new/changed health problems since you were last here?”

Specific Instructions for Recording Adverse Events

Investigators should use correct medical terminology/concepts when reporting AEs or SAEs. Avoid colloquialisms and abbreviations.

a. Diagnosis vs. Signs and Symptoms

If known at the time of reporting, a diagnosis should be reported rather than individual signs and symptoms (e.g., record only liver failure or hepatitis rather than jaundice, asterixis, and elevated transaminases). However, if a constellation of signs and/or symptoms cannot be medically characterized as a single diagnosis or syndrome at the time of reporting, it is ok to report the information that is currently available. If a diagnosis is subsequently established, it should be reported as follow-up information.

b. Deaths

All deaths that occur during the protocol-specified AE reporting period (see Section 5.1.2), regardless of attribution, will be reported to the appropriate parties. When recording a death, the event or condition that caused or contributed to the fatal outcome should be reported as the single medical concept. If the cause of death is unknown and cannot be ascertained at the time of reporting, report "Unexplained Death".

c. Preexisting Medical Conditions

A preexisting medical condition is one that is present at the start of the study. Such conditions should be reported as medical and surgical history. A preexisting medical condition should be re-assessed throughout the trial and reported as an AE or SAE only if the frequency, severity, or character of the condition worsens during the study. When reporting such events, it is important to convey the concept that the preexisting condition has changed by including applicable descriptors (e.g., "more frequent headaches").

d. Hospitalizations for Medical or Surgical Procedures

Any AE that results in hospitalization or prolonged hospitalization should be documented and reported as an SAE. If a subject is hospitalized to undergo a medical or surgical procedure as a result of an AE, the event responsible for the procedure, not the procedure itself, should be reported as the SAE. For example, if a subject is hospitalized to undergo coronary bypass surgery, record the heart condition that necessitated the bypass as the SAE.

Hospitalizations for the following reasons do not require reporting:

- Hospitalization or prolonged hospitalization for diagnostic or elective surgical procedures for preexisting conditions
- Hospitalization or prolonged hospitalization required to allow efficacy measurement for the study or
- Hospitalization or prolonged hospitalization for scheduled therapy of the target disease of the study.

e. Assessment of Severity of Adverse Events

The adverse event severity grading scale for the NCI CTCAE (v5.0) will be used for assessing adverse event severity. The below table should be used for assessing severity for adverse events that are not specifically listed in the NCI CTCAE.

Adverse Event Severity Grading Scale for Events Not Specifically Listed in NCI CTCAE

Grade	Severity
1	Mild; asymptomatic or mild symptoms; clinical or diagnostic observations only; or intervention not indicated
2	Moderate; minimal, local, or non-invasive intervention indicated; or limiting age-appropriate instrumental activities of daily living ^a
3	Severe or medically significant, but not immediately life-threatening; hospitalization or prolongation of hospitalization indicated; disabling; or limiting self-care activities of daily living ^{b,c}
4	Life-threatening consequences or urgent intervention indicated ^d
5	Death related to adverse event ^d

NCI CTCAE = National Cancer Institute Common Terminology Criteria for Adverse Events.

Note: Based on the most recent version of NCI CTCAE (v5.0), which can be found at: http://ctep.cancer.gov/protocolDevelopment/electronic_applications/ctc.htm

- a. Instrumental activities of daily living refer to preparing meals, shopping for groceries or clothes, using the telephone, managing money, etc.
- b. Examples of self-care activities of daily living include bathing, dressing and undressing, feeding oneself, using the toilet, and taking medications, as performed by patients who are not bedridden.
- c. If an event is assessed as a "significant medical event," it must be reported as a serious adverse event
- d. Grade 4 and 5 events must be reported as serious adverse events

f. Pregnancy

If a female subject becomes pregnant while receiving ocrelizumab or within 6 months after the last dose of study drug, a report should be completed and expeditiously submitted to the Genentech, Inc. Follow-up to obtain the outcome of the pregnancy

should also occur. Abortion, whether accidental, therapeutic, or spontaneous, should always be classified as serious, and expeditiously reported as an SAE. Similarly, any congenital anomaly/birth defect in a child born to a female subject exposed to the ocrelizumab should be reported as an SAE.

Additional information on any ocrelizumab-exposed pregnancy and infant will be requested by Genentech Drug Safety at specific time points (i.e. after having received the initial report, at the end of the second trimester, 2 weeks after the expected date of delivery, and at 3, 6, and 12 months of the infant's life).

g. Post-Study Adverse Events

The investigator should expeditiously report any SAE occurring after a subject has completed or discontinued study participation if attributed to prior ocrelizumab exposure. If the investigator should become aware of the development of cancer or a congenital anomaly in a subsequently conceived offspring of a female subject who participated in the study, this should be reported as an SAE adequately to Genentech drug Safety and the Sponsor.

h. Case Transmission Verification of Single Case Reports

The Sponsor agrees to complete the Case Transmission verification to ensure that all single case reports have been adequately received by Genentech via the Sponsor emailing Genentech a Quarterly line-listing documenting single case reports sent by the Sponsor to Genentech in the preceding time period.

The periodic line-listing will be exchanged within seven (7) calendar days of the end of the agreed time period. Confirmation of receipt should be received within the time period mutually agreed upon.

If discrepancies are identified, the Sponsor and Genentech will cooperate in resolving the discrepancies. The responsible individuals for each party shall handle the matter on a case-by-case basis until satisfactory resolution. The sponsor shall receive reconciliation guidance documents within the 'Activation Package'.

Following Case Transmission Verification, single case reports which have not been received by Genentech shall be forwarded by Providence Brain and Spine Institute to Genentech within five (5) calendar days from request by Genentech.

At the end of the study, a final cumulative Case Transmission Verification report will be sent to Genentech.

i. AEs of Special Interest (AESIs)

AESIs are a subset of Events to Monitor (EtMs) of scientific and medical concern specific to OCR, for which ongoing monitoring and rapid communication by the Investigator to the Sponsor is required. Such an event might require further investigation in order to characterize and understand it. Depending on the nature of the event, rapid communication by the trial Sponsor to other parties (e.g., Regulatory Authorities) may also be warranted.

There are no ocrelizumab Events of Special Interest.

Adverse events of special interest for this study include the following:

- Cases of potential drug-induced liver injury that include an elevated ALT or AST in combination with either an elevated bilirubin or clinical jaundice, as defined by Hy's law:
 - Treatment-emergent ALT or AST $> 3 \times$ ULN in combination with total bilirubin $> 2 \times$ ULN
 - Treatment-emergent ALT or AST $> 3 \times$ ULN in combination with clinical jaundice
- Data related to a suspected transmission of an infectious agent by the study drug (STIAMP), as defined below:

Any organism, virus, or infectious particle (e.g., prion protein transmitting transmissible spongiform encephalopathy), pathogenic or non-pathogenic, is considered an infectious agent. A transmission of an infectious agent may be suspected from clinical symptoms or laboratory findings that indicate an infection in a patient exposed to a medicinal product. This term applies only when a contamination of the study drug is suspected

j. Exchange OF Single Case Reports

Providence Brain and Spine Institute will be responsible for collecting all protocol-defined Adverse Events (AEs)/Serious Adverse Events (SAEs), AEs of Special Interest (AESIs), Special Situation Reports (including pregnancy reports) and Product Complaints (with or without an AE) originating from the Study for the Product.

Investigators must report all the above mentioned single case reports adequately to Genentech and the Sponsor within the timelines described below. The completed MedWatch reporting form should be faxed/mailed immediately upon completion to Genentech and the Sponsor at the following contacts:

All protocol-defined AEs, SAEs, AESIs, Special Situation Reports (including pregnancy reports) and Product Complaints with an AE should be sent to:

**[contact] or
Email: [contact]**

AND

**[contact] (Regulatory) and [contact] (Study Manager) or
Email: [contact] (Regulatory) and CC
[contact] (Study Manager)**

All Product Complaints without an AE should be sent to:

Email: [contact]

AND

**[contact] (Regulatory) and [contact] (Study Manager) or
Email: [contact] (Regulatory) and CC
[contact] (Study Manager)**

It is understood and agreed that the Sponsor will be responsible for the evaluation of AEs/SAEs, AESIs, Special Situation Reports (including pregnancy reports) and Product Complaints (with or without an AE) originating from the study. These single case reports will be exchanged between the parties as outlined below so that regulatory obligations are met.

Serious adverse events (SAEs), AEs of Special Interest (AESIs), pregnancy reports, other Special Situation Reports and Product Complaints (with or without an AE), where the patient has been exposed to the Genentech Product (OCR), will be sent on a MedWatch form to Genentech Drug Safety and to the Sponsor. Transmission of these reports (initial and follow-up) will be either electronically or by fax and within the timelines specified below:

- **Serious Adverse Drug Reactions (SADRs)**

Serious AE reports that are related to OCR shall be transmitted to Genentech and the Sponsor within fifteen (15) calendar days of the awareness date.

- **Other SAEs**

Serious AE reports that are unrelated to OCR shall be transmitted to Genentech and the Sponsor within thirty (30) calendar days of the awareness date.

- **AESIs**

AESIs shall be forwarded to Genentech and the Sponsor within fifteen (15) calendar days of the awareness date.

- **Special Situation Reports**

Pregnancy reports

While such reports are not serious AEs or Adverse Drug Reactions (ADRs) per se, as defined herein, any reports of pregnancy where the fetus may have been exposed to OCR, shall be transmitted to Genentech and the Sponsor within thirty (30) calendar days of the awareness date. Pregnancies will be followed up until the outcome of the pregnancy is known, whenever possible, based upon due diligence taken to obtain the follow-up information.

- **Other Special Situation Reports**

In addition to all SAEs, pregnancy reports and AESIs, the following other Special Situations Reports should be collected even in the absence of an Adverse Event and transmitted to Genentech and the Sponsor within thirty (30) calendar days:

- Data related to OCR usage during breastfeeding

- Data related to overdose, abuse, misuse or medication error (including potentially exposed or intercepted medication errors)

In addition, reasonable attempts should be made to obtain and submit the age or age group of the patient, in order to be able to identify potential safety signals specific to a particular population.

- **Product Complaints**

All Product Complaints (with or without an AE) shall be forwarded to Genentech and the Sponsor within fifteen (15) calendar days of the awareness date.

A Product Complaint is defined as any written or oral information received from a complainant that alleges deficiencies related to identity, quality, safety, strength, purity, reliability, durability, effectiveness, or performance of a product after it has been released and distributed to the commercial market or clinical trial.

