3. STUDY DESIGN

3.1 DESCRIPTION OF THE STUDY

This is a multicenter, prospective, open-label Phase IV clinical trial. Patients with relapsing forms of MS, ages 18 to 65, who have received a stable dose of NTZ for 12 or more consecutive months, and have been free of relapses, disability worsening or MRI progression 6 months prior to the transition screening visit will be eligible for the study. After informed consent to participate has been obtained, the patient will have a neurological exam, EDSS, 3T or 1.5T MRI, MSIS-29 and labs done for the screening visit to determine eligibility. 3T or 1.5T brain MRI with and without contrast will be performed with the standard MS protocol. It is preferred that the MRIs are done on a 3T scanner for this trial, but not required. MRIs will be performed with 3mm slice thickness with no gaps between slices. Patients will receive their first dose of OCR 4 to 6 weeks after the last dose of NTZ. Other baseline measures, including EDSS, MSIS-29, and labs will be performed within 4 weeks of screening. A neurological exam, EDSS, and labs will be performed at month 3, month 6, month 9, and month 12. MSIS-29 will be performed at months 6 and 12. MRIs will be performed at screening to determine

eligibility and at months 3, 6, and 12. All adverse events will be reported to the study sponsor. OCR will not be provided by the study; the medication will be supplied through the patient's commercial pharmacy and billed to the patient or the patient's insurance.

Patients will receive OCR 4-6 weeks after their last infusion of NTZ. OCR 300mg IV will be given on Day 0 and repeated with the same dose on Day 14±2. Patients will then receive OCR 600mg IV every 24 weeks.

If discontinuation of study drug occurs, the subject may continue in the trial for observational purposes. If willing to continue, they will complete all visit items moving forward, with the exception of study drug dosing and pregnancy testing (if applicable). If study drug is discontinued and the subject is unwilling to continue in the trial, a premature termination visit will be completed as soon as possible.

The target enrollment is 50 patients from 5 centers. Serious adverse events recorded during the trial will be reported to the study sponsor via Medwatch form.

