- Concomitant medications and adverse events (not required to be reviewed with the patient in person if Baseline is within 7 days of Screening visit, collect via chart review)
- OCR administration (300mg, 2 administrations: Day 0 and Day 14 ± 2 days)

Visit 3/3 Month Visit (Day 84 +/- 14 days from Baseline Day 0)

The following clinical and laboratory evaluations will occur 84 days from Baseline with a +/- 14 day window.

- Vital signs
- Neurological exam
- Relapse assessment
- EDSS
- Laboratory assessments: CBC, CMP, Pregnancy test (female only)
- MRI
- Concomitant medications and adverse events

Visit 4/6 Month Visit (Day 168 +/- 14 days from Baseline Day 0)

The following clinical and laboratory evaluations will occur 168 days from Baseline with a +/- 14 day window.

- Vital signs
- Neurological exam
- Relapse assessment
- EDSS
- MSIS-29
- Laboratory assessments: CBC, CMP, Pregnancy test (female only)
- MRI
- Concomitant medications and adverse events
- OCR administration (600mg)

Visit 5/9 Month Visit (Day 252 +/- 14 days from Baseline Day 0)

The following clinical and laboratory evaluations will occur 252 days from Baseline with a +/- 14 day window.

- Vital signs
- Neurological exam
- Relapse assessment
- EDSS
- Laboratory assessments: CBC, CMP, Pregnancy test (female only)
- Concomitant medications and adverse events

Visit 6/12 Month Visit (Day 336 +/- 14 days from Baseline Day 0)

The following clinical and laboratory evaluations will occur 336 days from Baseline with a +/- 14 day window.

- Vital signs
- Neurological exam
- Relapse assessment
- EDSS
- MSIS-29
- Laboratory assessments: CBC, CMP, Pregnancy test (female only)
- MRI
- Concomitant medications and adverse events
- OCR administration (600mg)

End of Study (EOS) Phone Contact (30 days +/- 14 days from study discontinuation)

The following clinical evaluation will occur 30 days +/- 14 days from study completion (12 Month OCR administration) or premature termination visit:

- Adverse events

Premature Termination Visit

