4.6 DISCONTINUATION OF THERAPY

OCR therapy must be discontinued for any of the following reasons:

- Life-threatening IRR or serious hypersensitivity reaction
- Active hepatitis B infection
- PML
- Active TB, either new onset or reactivation
- HIV
- Patient becomes pregnant
- Unacceptable toxicity
- Patient election to discontinue therapy (for any reason)

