5. REPORTING OF ADVERSE EVENTS

An AE is an unfavorable unintended sign, symptom, or disease that is experienced by the patient, whether or not there is a causal relationship with OCR. At the time of consenting, each patient will be given the names and telephone numbers of the study personnel for reporting AE's. The investigator must conduct thorough assessment to determine the severity of the AE and the relationship to the study drug. Any clinically significant AE of severity moderate or higher, requires follow up until resolution or stabilization by the treating investigator beyond the end of study contact.

All AEs should be recorded in the patient's AE case report form regardless of severity or relationship to the study drug. The investigator must review the laboratory findings for significance (all out of range values must be assessed as clinically significant or not clinically significant) and sign and date the laboratory report. All clinically significant laboratory findings must be reported as adverse events.

Any severe laboratory abnormalities that are considered serious should be reported to the coordinating center as outlined below.

All SAEs must be reported by the investigator to Genentech by email [contact] or [contact] and Providence Regional Research Regulatory Office by email [contact] (Regulatory) and CC [contact] (Study Manager) or fax to [contact] (Regulatory) and [contact] (Study Manager) within 24 hours of the investigator's knowledge of the event.

Severity

The intensity of severity of an AE will be graded as follows:

Mild	Symptoms(s) barely noticeable to subject or does not make subject uncomfortable; does not influence performance or functioning; prescription drug not ordinarily needed for relief of symptoms(s) but may be given because of personality of subject
Moderate	Symptom(s) of a sufficient severity to make subject uncomfortable; performance of daily activity is influenced; subject is able to continue in study; treatment for symptom(s) may be needed.
Severe	Symptom(s) cause severe discomfort; symptoms cause incapacitation or significant impact on subject's daily life; severity may cause cessation of treatment with investigational drug; treatment for symptom(s) may be given and/or subject hospitalized.

Relationship to Study Drug

The relationship or association of the AE to a study drug will be characterized as follows:

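### Section 3.1 waives scheduled pregnancy tests for every patient who stops OCR and stays, inside the 6-month post-dose period in which 5.3 f makes a pregnancy reportable

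*Combined protocol and SAP*

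**What the plan says.** Section 5.3 f (Pregnancy) sets the reportable period: "If a female subject becomes pregnant while receiving ocrelizumab or within 6 months after the last dose of study drug". A report then goes to the drug's manufacturer and the pregnancy is followed to its outcome. Section 5.3 j lists pregnancy reports under special situations and counts the reporting time from the date of awareness.

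Section 3.1 deals with patients who stop OCR but agree to stay: "they will complete all visit items moving forward, with the exception of study drug dosing and pregnancy testing (if applicable"). It sets no time limit and does not depend on why OCR was stopped.

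Section 4.5.1 and Appendix A schedule a test at months 3, 6, 9 and 12: "Laboratory assessments: CBC, CMP, Pregnancy test (female only"). OCR is due at months 6 and 12 but not at months 3 and 9. The premature termination visit, for patients who leave, also includes the test. At unscheduled visits it is done if indicated.

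Pregnancy is one of eight listed reasons in 4.6 for which OCR must be stopped ("Patient becomes pregnant"). Inclusion criterion 7 requires contraception during the study.

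**The concern.** The plan treats a pregnancy in the 6 months after the last dose as an exposed pregnancy worth reporting and following. For one group it then removes the only scheduled item that would detect such a pregnancy directly, at visits the patient attends anyway.

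The waiver is natural for a woman who stopped because she is pregnant. It is written for all stoppers, including those who stop for toxicity or by choice, and applies from the day they stop.

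What is at stake is how completely exposed pregnancies are captured, and how early. No efficacy endpoint or analysis depends on it.

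**Working it through.** The plan states no figure to reproduce. The check sets the visit calendar against the reportable period.

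**Inputs.** OCR doses on Day 0, Day 14 ± 2, then every 24 weeks, so Day 168 and Day 336 (3.1, 4.5.1). Visits with a scheduled test on Days 84, 168, 252 and 336, each ± 14 days (4.5.1, Appendix A). Reportable period of 6 months after the last dose (5.3 f). The plan does not give 6 months in days; 183 is assumed, with 168 and 180 as alternatives.

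**Formulas.** End of period = last dose day + 183. A visit lies inside if visit day − last dose day ≤ 183. The range for each gap takes the earliest visit with the latest dose, and the reverse.

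**Last dose Day 14, patient stays.** The period ends on Day 14 + 183 = 197.
- Day 84 visit: 84 − 14 = 70 days after the dose; range 70 − 16 = 54 to 98 − 12 = 86. Inside.
- Day 168 visit: 168 − 14 = 154 days; range 154 − 16 = 138 to 182 − 12 = 170. Inside.

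If only the Day 0 dose was given, the period ends on Day 183, and nominal Days 84 and 168 are again inside.

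**Last dose Day 168, patient stays.** The period ends on Day 168 + 183 = 351.
- Day 252 visit: 252 − 168 = 84 days; range 238 − 182 = 56 to 266 − 154 = 112. Inside.
- Day 336 visit: 336 − 168 = 168 days; range 322 − 182 = 140 to 350 − 154 = 196. Nominally inside; a late visit can fall outside.

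**Sensitivity to the day count.** With 180 days the periods end on Days 194 and 348; with 168 days, on Days 182 and 336. The same nominal visits are inside each time, although with 168 days the Day 336 visit falls on the last day.

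**Result.** Up to two scheduled tests per woman who stops and stays are waived inside the reportable period.

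**Comparison groups.**
- A woman with the same last dose date who remains on OCR is tested at those visits. At months 3 and 9 this cannot be a check immediately before an infusion, because none is due.
- A woman who stops and leaves is tested at premature termination.
- Only the woman who stops and stays has no scheduled test.

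**How many women.** The plan does not give the number of women of childbearing potential. The target is 50 patients of both sexes, aged 18 to 65. If side-effect withdrawal matched the 3.2% and 3.8% cited in 3.2, then 50 × 0.032 = 1.6 and 50 × 0.038 = 1.9, or about 2 patients. The 10% attrition allowance in 4.9.6 is 50 × 0.10 = 5. Neither figure measures stop-and-stay directly, and only women of childbearing potential among those who stay count. None to a few is a reasonable expectation.

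**The case against.** The strongest reply is that no rule is broken. Section 5.3 f is a duty to report, 5.3 j starts the clock at awareness, and 5.3 g uses the same model after the study. Nowhere does the plan promise active ascertainment for 6 months. That stands. A reader might infer that 3.1 contradicts 5.3 f; it does not. It makes pregnancies that 5.3 f covers harder to notice.

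A second reply is that the tests may exist to trigger the stopping rule in 4.6, a purpose that ends once OCR has stopped. The plan gives no reason for the tests, so this may well explain the waiver. It does not answer the point that 5.3 f keeps its interest in these women for 6 months more.

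Third, safeguards remain. Contraception is required, adverse events and all medications are reviewed at each visit, unscheduled tests are possible, and at consent "each patient will be given the names and telephone numbers of the study personnel for reporting" AEs. Pregnancy also appears among the AE recording instructions, and the wording "Examples of non-directive questions include" leaves sites free to ask more. All this lowers the weight, but none of it is a scheduled test or a stated pregnancy question. The phrase about applicability in 3.1 most naturally refers to women of childbearing potential and does not restore testing.

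A reader might also extend the point to completers. Their last test is at Month 12, and the EOS call, for which "The following clinical evaluation will occur 30 days +/- 14 days from study completion (12 Month OCR administration) or premature termination visit", lists adverse events only. With the last study dose on Day 336 and the call at 30 days, 183 − 30 = 153 post-dose days follow the last planned contact. The documents do not make this an error. Reporting after the study is awareness-based by design, OCR is standard care that may continue, and the consent pages, which may tell patients to report a pregnancy, are not in the file.

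**Conclusion.** The point holds for patients who stop OCR and stay, and only for them. Up to two scheduled pregnancy tests per woman are waived inside the period in which 5.3 f makes a pregnancy reportable, and nothing elsewhere in the plan restores them.

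The gap is minor. It concerns safety ascertainment, probably affects none to a few women, and leaves every endpoint and analysis unchanged. It is still worth correcting, because an explicit rule produces it and the visits take place anyway.

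The conclusion rests on 6 months being about 168 to 183 days, on visits near their nominal days, and on reading the waiver as it is written, for all stoppers.

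**What to change.** In 3.1, waive the pregnancy test only at visits more than 6 months after the last OCR dose, or where the pregnancy is already known. State the 6 months in days and repeat the rule in the pregnancy-test note of Appendix A. Alternatively, keep the waiver and ask pregnancy status directly at each observation visit inside the 6 months.

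Optionally, add the same question to the EOS call. For completers it would cover only about the first 30 post-dose days; the later 153 or so would stay awareness-based.

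The cost is up to two urine tests per woman who stops and stays, or one question at each of those visits. Appendix A already marks these tests as study-paid at months 3, 6, 9 and 12. It adds a small burden for women no longer on OCR, and under 3.5 the amendment needs approval by the sponsor's IRB and each site's IRB or ethics committee, with 5 centers planned.
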